8.2.2. Efficacy Criteria

The primary efficacy endpoint will be the change in MADRS total score from Baseline (i.e., the start of double-blind treatment) to the end of the double-blind treatment period (i.e., Week 6). The primary comparisons will be between each MIN-117 dose group (5.0 mg and 2.5 mg) and the placebo group.

The key secondary endpoint will be the change from Baseline in HAM-A, and it will be evaluated similar to the primary efficacy endpoint. Change from Baseline in CGI-S and observed CGI-I scores will also be evaluated as measures of the clinical meaningfulness of the changes in the objective measures of depression and anxiety. The primary comparisons will be between each MIN-117 dose groups (5.0 mg and 2.5 mg) and the placebo group.

The change from Baseline for the remaining efficacy endpoints will be analysed similarly to primary endpoint.

Time to onset of antidepressant effect will include criteria of sustained pre-defined decrease in depressive symptomatology and will be analysed using conditional survival analysis.

In order to establish the clinical relevance of the primary analysis results, the rate of responders defined as a MADRS score of $\geq 50\%$, will be calculated at each assessment between Week 1 and Week 6 and the 95% confidence interval for the odds ratio of MIN-117 versus placebo computed using a logistic regression model.

Time to clinical response (first assessment with a $\geq 50\%$ improvement from Baseline in total MADRS score scale) will be analysed using a survival analysis method assuming proportional hazard. Time to $\geq 30\%$ will also be explored.

The rate of early and sustained full responders ($\geq 50\%$ improvement from Baseline in total MADRS score and a CGI-I score ≤ 2 at every time points) and the rate of remission in MADRS (defined as a score < 12) will be analysed using the same method as for the clinical response. The rate of early and sustained response based on $\geq 30\%$ will also be explored.

The following efficacy evaluations will be performed at the scheduled visits according to the time points provided in the [Time and Events Schedule](#) in the following order and in the morning (between 8:00 a.m. to 1:00 p.m.) during the 6-week, double-blind treatment phase, as applicable:

- MADRS
- CGI-S
- CGI-I
- HAM-A
- IDS-SR₃₀
- SHAPS
- PSS
- A-SEX
- DSST

8.3. Pharmacokinetic Evaluations

8.3.1. Sample Collection and Handling

Blood samples (6 mL) will be collected for assessing the plasma concentration of MIN-117 [REDACTED] during the Double-blind Treatment Period at Visits 2, 3, 4, and 5, at pre-dose (within 1 hour from dosing) and approximately 2 to 4 hours post-dose (approximate time of maximum plasma concentration for MIN-117). Additionally one sample will be collected at the post-study follow-up visit (Visit 6).

The actual time and date of the blood draw and actual date and time of the last study drug administration prior to collection of the PK sample must be accurately recorded on eCRF.

8.3.2. Analytical Procedures

Plasma samples will be analyzed to determine concentrations of MIN-117 [REDACTED] [REDACTED] using validated, specific, and sensitive liquid chromatography-mass spectrometry (LC-MS/MS) methods under the supervision of the sponsor's bioanalytical facility or designee.

Plasma samples will be disposed after the clinical study report is finalized.

8.3.3. Pharmacokinetic Evaluations

Plasma levels of MIN-117 [REDACTED] will be tabulated.

Population pharmacokinetic analyses will be performed on the data of this study in combination with data pooled from other studies. An objective of these analyses is to investigate the potential effects of covariates, such as demographics and concomitant drugs, on the pharmacokinetics of MIN-117 [REDACTED]. An integrated population pharmacokinetic model for MIN-117 will be used combining the data sets of Phase 1 and 2 studies. Standard population pharmacokinetic parameters will be estimated. The effects of demographic characteristics, concomitant medications, laboratory values, and other covariates on MIN-117 pharmacokinetics will be evaluated. Results of the population pharmacokinetic analysis will be presented in a separate report.

8.4. Pharmacodynamic Evaluations

Blood samples will be collected for pharmacodynamic assessment of BDNF, GDNF, VEGF, IGF-1, fibroblast growth factor-2, C-reactive protein, cortisol, amyloid-A, IL-1 β , IL-6, and IL-10 at Baseline and the Week 6 visit.

8.5. Pharmacogenomic Evaluations

A pharmacogenomic blood sample (10 mL) will be obtained (at sites where local regulations permit) at Visit 2 or any time during the double-blind phase to allow for pharmacogenomic research, as necessary. Pharmacogenomic research may be performed to explain variability in the data or to address emerging clinical issues. Candidate genes from previous pharmacogenomic studies conducted by the Sponsor on similar compounds may be analyzed as well as genes known to be associated with depression or response to anti-depressive treatment [e.g., serotonin transporter gene promoter polymorphism (5-HTTLPR)]. Patients will also be asked for consent for storage of their DNA sample for future research.

8.6. Safety Evaluations

Any clinically significant abnormalities persisting at the end of the study will be followed by the investigator until resolution or until a clinically stable endpoint is reached.

The study will include the following evaluations of safety and tolerability according to the time points provided in the [Time and Events Schedule](#)

Adverse Events

Adverse events will be reported by the patient for the duration of the study. Adverse events will be followed by the investigator as specified in [Section 11](#), Adverse Event Reporting.

Clinical Laboratory Tests

Blood samples for serum chemistry (collected after an overnight fast) and hematology and urine samples for urinalysis will be collected according to the Time and Events Schedule. In women of childbearing potential, a serum pregnancy will be performed at Screening, Baseline, Visit 5/Early Withdrawal, and EOS visit. In addition, urine sample for drug and alcohol testing and urine samples from women of childbearing potential for pregnancy testing will be collected (refer to the Time and Events Schedule). The investigator must

review the laboratory report, document this review, and record any clinically relevant changes occurring during the study in the adverse event section of the eCRF. The following tests will be performed:

- **Hematology:**
 - hemoglobin
 - hematocrit
 - white blood cell (WBC) count with differential
 - platelet count
 - red blood cell (RBC) count
- **Serum Chemistry:**
 - sodium
 - potassium
 - chloride
 - blood urea nitrogen (BUN)
 - creatinine
 - glucose (fasting)
 - AST
 - ALT
 - total bilirubin
 - alkaline phosphatase
 - gamma-glutamyl transferase (GGT)
 - creatine phosphokinase (CPK)
 - lactic acid dehydrogenase (LDH)
 - uric acid
 - calcium
 - phosphorous (inorganic)
 - albumin
 - total protein
 - cholesterol (total)
 - triglycerides
 - high density lipoprotein (HDL)
 - low density lipoprotein (LDL)
 - thyroid-stimulating hormone (TSH) (at Screening only)
- **Urinalysis**
 - Dipstick**
 - specific gravity
 - pH
 - glucose
 - protein
 - blood
 - ketones
 - bilirubin
 - urobilinogen
 - nitrite
 - leukocyte esterase
 - Sediment** (if dipstick result is abnormal)
 - RBC
 - white blood cell (WBC)
 - epithelial cells
 - crystals
 - casts
 - bacteria

If dipstick result is abnormal, the sediment will be examined microscopically.

- Serum Pregnancy Testing for women of childbearing potential: at Screening, Baseline (Visit 2) and Post study Visit (Visit 6).
- Urine Pregnancy Testing for women of childbearing potential only: at Baseline (Visit 2), Visits 4, 5 and 6.

If results of the pregnancy test(s) are positive, the patient will be excluded or withdrawn from the study. Of note, at Baseline (Visit 2), both a urine and a serum pregnancy test will be performed. Enrollment will be based on the result of the urine test performed locally in

order not to postpone the randomization. Nevertheless, this urine pregnancy test will have to be confirmed by the serum pregnancy test assessed centrally. Should there be a discrepancy in the results, the result of serum test will prevail.

- Serology (HBsAg, HCV antibody, and HIV antibodies 1 and 2).
- Urine Drug Screen and Urine Alcohol: Potential patients will be tested for drugs of abuse (cocaine, methadone, amphetamines, cannabinoids, opiates, benzodiazepines, barbiturates, tricyclic antidepressants) and alcohol according to the [Time and Events Schedule](#). If the results of the urine drug screen (except for prescription benzodiazepines, prescription barbiturates, prescription tricyclic antidepressants or prescription opiates at Screening) or the urine alcohol test are positive at Screening or Baseline, the patient will not be enrolled. If the screen is positive for cannabinoids, they will be excluded.

Electrocardiogram (ECG)

Triplicate ECGs will be performed according to the Time and Events Schedule. The visits, three 12-lead ECGs will be recorded at least 1 minute apart within 5 minutes after the patient is supine for at least 10 minutes. ECG assessments during the double-blind phase should occur prior to the post-dose PK sample.

Twelve-lead ECGs will be recorded at a paper speed of 25 mm per second until 4 regular consecutive complexes are available.

The following intervals will be assessed: RR, PR, QRS, and QT. Electrocardiogram monitoring will include the evaluation of lengthening of the QTc interval using QTcF.

Vital Signs

Vital signs will include oral/aural temperature, respiratory rate, pulse, and blood pressure.

Three consecutive blood pressure and pulse readings will be taken at each visit. Blood pressure and pulse should be taken in the arm with the highest pressure, using the same arm for each reading and for all visits. An appropriately sized arm cuff will be used, and the size of the cuff should remain constant for all visits.

Blood pressure and pulse will be taken after the patient has been resting quietly in supine position for 5 minutes. Vital signs assessments during the double-blind phase should occur prior to the post-dose PK sample, and after the ECG assessments.

Physical Examination

Physical examinations, height, and weight will be performed at the times specified in the Time and Events Schedule.

Any abnormalities present at Baseline, or subsequent changes, will be documented in the appropriate sections of the CRF. Any clinically significant abnormalities persisting at the end of the study will be followed by the investigator until resolution or until reaching a clinically stable endpoint.

Columbia Suicide Severity Rating Scale (C-SSRS)

Emergence of suicidal ideation will be assessed using the C-SSRS, a prospective rating scale that tracks both treatment-emergent suicidal ideation and behaviors, and will be

performed at the times specified in the [Time and Events Schedule](#). The C-SSRS has been used frequently in clinical studies, is a standard measure for suicidal ideation assessment, and its use is in accordance with FDA guidance.

See [Attachment 11](#) for an example of this scale.

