1.2. MIN-117 Pharmacological Profile and Rationale as a Unique Antidepressant

MIN-117 is an investigational antidepressant belonging to a new chemical class, the benzofuran derivatives. The chemical designation is (2*S*)-1-[4-(3,4-Dichlorophenyl)piperidin-1-yl]-3-[2-(5-methyl-1,3,4-oxadiazol-2-yl)benzo[*b*]furan-4-yloxy]propan-2-ol monohydrochloride. MIN-117 is characterized by its affinity for 5-HT_{1A} pre-synaptic autoreceptors and 5-hydroxytryptamine transporters (5-HTT). The K_i values for 5-HT_{1A} receptors and 5-HTT of human were 5.0 and 0.81 nmol/L, respectively. MIN-117 acts as a serotonin reuptake inhibitor. In addition, MIN-117 has high affinity for adrenergic alpha (α)₁ and serotonergic 5-HT_{2A} and acts as antagonist to each receptor. MIN-117 is also active as a dopamine transport (DAT), by inhibiting reuptake of dopamine from the synaptic cleft. Furthermore, MIN-117 has moderate affinity for 5-HT_{2C} and also acts as a moderate norepinephrine transporter (NET) inhibitor.

For the most accurate and current information regarding the efficacy and safety of MIN-117, refer to the latest version of the Investigator's Brochure for MIN-117.

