In the SON-117-C01 study, 132 TEAEs were reported (40 with placebo, 40 with MIN-117 1 mg, 22 with MIN-117 3 mg and 30 with MIN-117 7.5 mg). The body systems most frequently affected were the Nervous system (36), Skin and subcutaneous system (26), and Gastrointestinal system (23). The most frequently reported TEAEs were headache (15 episodes: 7 with placebo, 1 with MIN-117 1 mg, 2 with MIN-117 3 mg and 5 with MIN-117 7.5 mg dose) and insomnia (10 episodes; 5 with placebo, 2 with 1 mg dose, 1 with 3 mg dose and 2 with 7.5 mg dose). All TEAEs were mild or moderate in intensity. Only 1 TEAE was rated as severe (fatigue, MIN-117 7.5 mg).

Among the reported TEAE, 62 were considered related to the study drug: 22 with placebo (66.7% of the subjects) and 40 with MIN-117: 22 with MIN-117 1 mg (60% of the subjects); 8 with MIN-117 3 mg (40% of the subjects) and 10 with MIN-117 7.5 mg (44% of the subjects).

The most frequently reported ADRs were insomnia (9 episodes: 5 with placebo, 1 with MIN-117 1 mg; 1 with MIN-117 3 mg and 2 with MIN-117 7.5 mg), headache (6 episodes: 5 with placebo and 1 with MIN-117 1 mg) and diarrhea (5 episodes: 2 with placebo, 2 with MIN-117 1 mg and 1 with MIN-117 7.5 mg).

Of note, in the SON-117-C01 study, escitalopram was administered as a positive control to 9 subjects. In this group, 28 ADRs were reported (88.9% of the subjects). The most frequently reported ADRs were asthenia (5 episodes) and headache (3 episodes).

Results on the SSRI withdrawal scale indicated that there were no more self-perceived adverse events with MIN-117 than with placebo or escitalopram.

No significant biological abnormalities were evidently related to MIN-117.

Repeated doses of MIN-117 induced no clinically relevant changes in blood pressure. All mean values of supine systolic and diastolic blood pressure as well as heart rate were within the normal range. There was a trend toward a slight decrease in supine DBP with MIN-117 3 mg (Day 1, Day 14 and Day 18) when compared to placebo. The incidence of abnormal orthostatic tests was also higher with MIN-117 3 mg, although none of them were symptomatic. Heart rate tended to increase following MIN-117 3 mg administration. This

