6. DOSAGE AND ADMINISTRATION

On Day 1 (Visit 2) of the double-blind treatment phase, patients will be randomized to receive placebo, 5.0 mg MIN-117, or 2.5 mg MIN-117, PO, once daily for 6 weeks (Table 1).

Study drugs will be packaged using a double-dummy, double-blind design. The study drugs will be packaged in individual patient kits containing 6 weekly blisters, with each blister containing medication sufficient for 8 days (1 week of treatment and 1 day of overage). Medications blisters will be dispensed to the patients at Visit 2 (3 blisters), Visit 3 (2 blisters), and Visit 4 (1 blister) to ensure intra-visit daily dosing, including the allowed visit windows (± 3 days), are covered. Daily dose will consist of 2 capsules containing the intended dose (MIN-117 or Placebo). MIN-117 capsules are available in 2.5 mg strength.

Table 1: Characteristics of the Treatment and Dosage

Treatment	Capsule Strength / Number		Total Number of Capsules	
	No. of MIN 2.5 mg capsules	No. of MIN-117 placebo capsules	During Study Participation	Total Capsules Dispensed
5.0 mg MIN-117	2	-	84	96
2.5 mg MIN-117	1	1	84	96
Placebo	-	2	84	96

Placebo and MIN-117 capsules are identically matched in appearance.

The study drug should be administered in a single dose in the morning at approximately the same time each day with or without food per patient's food intake habit. Capsules should be swallowed whole with water and not divided, crushed, chewed, or placed in water.

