5.4.4. Other Safety Analyses

Descriptive summaries of vital signs data including body temperature, pulse, respiratory rate, and blood pressure (systolic and diastolic) and respective changes from Baseline, will be presented by time point and treatment group. The number and percentage of patients with PCS vital signs per the table below, as determined in the eCRF, occurring post-baseline will

also be summarized by time point and treatment group. All vital signs will be listed with clinically significant values flagged, as well as for patients with any PCS results.

CRITERIA FOR POTENTIALLY CLINICALLY SIGNIFICANT VITAL SIGNS

Parameter	Flag	Criteria
		Observed Value
Systolic blood pressure (mm Hg)	High	≥ 150
	Low	≤ 90
Diastolic blood pressure (mm Hg)	High	≥ 100
	Low	≤ 50
Pulse rate (bpm)	High	≥ 110
	Low	≤ 50
Temperature (°C)	High	≥ 38
	Low	< 35

Electrocardiogram (ECG) variables and their change from baseline will be summarized with descriptive statistics by time point and treatment group. ECG variables will include heart rate, PR interval, QRS interval, QT interval, and QTc interval corrected for heart rate using QTcF. QTcF values will also be tabulated for their absolute values and tabulated relative to baseline measurements in order to detect individual QTcF changes. Additionally, the number and percentage of patients with PCS values defined in the table below

Use header of the convention table for all relevant safety parameters.

Criteria for Potentially Clinically Significant ECG Parameters

Parameter	Flag	Criteria	
		Observed Value	Change from Baseline or Observed Value
Heart Rate (bpm)	High	> 110	
	Low	≤ 50	

QTcF ^a Interval (msec)	High Male	> 450	30-60, > 60, > 500
	High Female	> 470	
QRS Interval (msec)	High	> 120	
PR Interval (msec)	High	> 220	

^a QTc interval (Fridericia's) is derived as: $QTcF = QT \text{ Interval (msec)} / (RR \text{ (msec)/1000})^{1/3}$

For these summaries, worst-case assignments will be made to ensure patients with such values are not counted more than once. For example, a patient with QTcF interval > 500 msec will count once in the > 500 msec category and will not appear in the > 450 or > 480 msec categories. Similar conventions will be used for the 30 to 60 and > 60 msec categories. All ECG analyses will be based on the average of triplicate measurements.

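### Blood pressure and pulse are taken supine only, so asymptomatic orthostatic change cannot be systematically detected or quantified, although an earlier study found more abnormal orthostatic tests at 3 mg

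*Protocol*

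**What the plan says.** **Measurement.** Protocol Section 8.6 (Vital Signs) states: "Three consecutive blood pressure and pulse readings will be taken at each visit". It then sets the posture: "Blood pressure and pulse will be taken after the patient has been resting quietly in supine position for 5 minutes". The same text places vital signs after the ECG and before the post-dose PK sample. The Time and Events Schedule, in both the protocol and SAP Section 1.2, has a single row for vital signs, temperature and weight, and its footnotes add no standing measurement.

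**Analysis.** Protocol Section 10.8.3 and SAP Section 5.4.4 summarise systolic pressure, diastolic pressure and pulse as values and changes from Baseline. The SAP table of potentially clinically significant (PCS) values sets limits on single observed values and has no postural row.

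**Background.** Protocol Section 1.2 says that the drug "has high affinity for adrenergic alpha"-1 and 5-HT2A receptors and "acts as antagonist to each receptor". The Safety part of Section 1.4 reports on the 14-day study in healthy men (SON-117C01): "The incidence of abnormal orthostatic tests was also higher with MIN-117 3 mg, although none of them were symptomatic". The same paragraph opens with the overall judgement: "Repeated doses of MIN-117 induced no clinically relevant changes in blood pressure".

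**Doses here.** Under Protocol Section 6, "patients will be randomized to receive placebo, 5.0 mg MIN-117, or 2.5 mg MIN-117, PO, once daily for 6 weeks".

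**The concern.** An orthostatic change is the difference between a lying and a standing reading. If every reading is taken lying down, that difference does not exist in the data and no analysis can recover it.

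The protocol gives three reasons why someone might want it: the alpha-1 antagonism, the more frequent abnormal orthostatic tests at 3 mg, and the position of 3 mg between the 2.5 mg and 5.0 mg arms. Safety of both doses is a stated secondary objective (Protocol Section 2). As planned, the vital-sign tables would look the same whether or not the orthostatic result from SON-117C01 recurs. The other route, adverse events reported by patients, is poorly suited to a change that caused no symptoms in any case in that study.

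The trial also goes beyond the earlier exposure. Protocol Section 3.1 describes tolerability up to 7.5 mg for 14 days and up to 2.5 mg for 6 weeks, so it cites no 6-week experience at 5.0 mg. SON-117C01 enrolled healthy men. This trial takes patients of both sexes up to age 65, and Attachment 1 allows chronic use of some antihypertensives and diuretics.

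**Working it through.** The plan states no orthostatic figure, so there is nothing to reproduce. The check sets the sections side by side, then adds a small illustration.

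**1. How many postural differences are planned?** Each needs one supine and one standing reading at the same visit.
- Supine readings per visit: 3 (Section 8.6).
- Standing readings per visit: 0 (Section 8.6; Time and Events Schedule).
- Postural differences per patient: 0, in every arm.

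**2. Could the existing PCS limits stand in for a postural criterion?** SAP Section 5.4.4 flags systolic pressure at 150 or more or 90 or less, and diastolic pressure at 100 or more or 50 or less. Take readings in whole mmHg. Even if a standing value were collected, systolic pressure could fall from 149 to 91 without a flag (149 − 91 = 58 mmHg), and diastolic pressure from 99 to 51 (99 − 51 = 48 mmHg). The limits concern level, not change on standing. A separate criterion is needed as well as a separate reading.

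**3. What exactly was seen before?**
- Human: abnormal orthostatic tests more frequent at 3 mg, without counts or a definition of abnormal, and none symptomatic. At the same dose supine diastolic pressure tended to fall. The largest Day 1 heart-rate change, at 12 hours, was +15.6 against +1.083 on placebo (Section 1.4). The rise at 7.5 mg was less marked.
- Study size: 29 subjects received MIN-117 over three doses. The percentages with related events (60%, 40%, 44%) fit groups of 10, 10 and 9 (6/10, 4/10, 4/9), so about 10 men had 3 mg. This is an inference, not a stated figure.
- Animal (Section 1.3.2): in the rabbit tilt test, pressures fell at 300 mg/kg oral, and diastolic pressure was low at 12 hours at 100 mg/kg oral. There was no effect at intravenous doses up to 1 mg/kg.

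**4. What would standing readings offer?** This is an illustration under assumed rates, because the documents give none. It takes all 81 patients planned for one dose arm as measured.
- Chance of seeing at least one case, 1 − (1 − p)^81: 56% at p = 1%, 81% at 2%, 98% at 5%, over 99.9% at 10%.
- No case in 81: one-sided 95% upper bound = 1 − 0.05^(1/81) = 3.6%.
- Precision of a difference between 81 on one dose and 162 on placebo, 1.96 × √[p1(1 − p1)/81 + p0(1 − p0)/162], with p0 = 5%: p1 = 10% gives ±7.3 points, 15% gives ±8.5, 20% gives ±9.3.

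Precision is the relevant measure because the planned vital-sign tables are descriptive. Power for a significance test does not bear on them.

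**The case against.** The strongest reply is that the signal is thin. It comes from about 10 healthy men at one dose. The protocol judged the blood pressure changes not clinically relevant, does not flag the higher 7.5 mg dose for abnormal orthostatic tests, and describes that dose as well tolerated. The rabbit effects need very large oral doses: assuming a 70 kg patient, 5 mg is about 0.07 mg/kg (5/70), a crude comparison that ignores exposure. In the 6-week patient study, which included 2.5 mg, neither withdrawal for an adverse event was on MIN-117. Symptomatic postural events would be recorded as adverse events, as dizziness was in that study.

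All of this stands, and it limits the point to a cheap improvement. It does not supply the missing measurement. A judgement made on a small group of healthy men does not settle the matter for about 162 treated patients. The heart-rate effect did not increase steadily with dose, so tolerability at 7.5 mg does not by itself clear the range from 2.5 to 5.0 mg.

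A reader might infer three stronger things that the documents do not support:
- *That the protocol reports orthostatic hypotension.* It reports abnormal orthostatic tests without a criterion. The test could have been partly or wholly based on pulse.
- *That this was the only blood pressure signal in the earlier human data.* The same paragraph reports a slight downward trend in supine diastolic pressure, which the planned readings do cover. The text available to me also lacks part of the Section 1.4 safety account, so the single-dose findings could not be checked.
- *That the trial is blind to every postural problem.* Symptomatic events remain reportable. Only asymptomatic change is unmeasured.

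**Conclusion.** The point holds in its limited form. All planned blood pressure and pulse readings are supine, and neither the schedule nor the planned analyses contain a postural measure. The trial therefore cannot systematically detect or quantify asymptomatic orthostatic change. That is the kind of finding reported at 3 mg, between the two trial doses, for a drug described as an alpha-1 antagonist. In the text I could read, no reason is given for leaving the measurement out.

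The gap is complete for this quantity (zero planned differences), but its clinical size is unknown. The documents give no orthostatic rates, and the detection and precision figures above rest on assumed ones. The conclusion does not depend on those figures. It does not say that the drug causes orthostatic hypotension or that either dose is unsafe. It says that clean vital-sign tables from this trial could not be read as evidence on the question.

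**What to change.** - **Protocol Section 8.6:** add one standing blood pressure and pulse reading directly after the supine set, at Baseline (before the first dose) and at Visits 3, 4 and 5. Fix the standing time in the protocol and record time since the last dose. Vital signs need only precede the post-dose PK sample, so their timing relative to dosing can vary. Section 8.3.1 already requires the last dose time to be recorded for PK at these visits.
- **Protocol Section 10.8.3 and SAP Section 5.4.4:** add a descriptive summary of supine-to-standing change in systolic pressure, diastolic pressure and pulse, by arm and visit. Say which supine value is used, for example the mean of the three.
- **SAP PCS table:** add a treatment-emergent orthostatic row, counting a patient only if the criterion was not met at Baseline. The sponsor should state the criterion before unblinding.

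The cost is a few extra minutes at each of four visits, at least three eCRF fields (standing systolic, diastolic and pulse) and one table, with the same cuff, staff and visits. If the sponsor prefers not to add the reading, the protocol should say why, and the study report should state that postural change was not assessed.
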